## **5.0 METHODOLOGY**

### **5.1 Entry Criteria**

#### **5.1.1 Diagnosis/Condition for Entry into the Trial**

All subjects must have a diagnosis of ALL of either B-cell, T-cell, or mixed (i.e., B/T) lineage.

#### **5.1.2 Subject Inclusion Criteria**

In order to be eligible for participation in this trial, the subject must:

1. Be willing and able to provide written informed consent for the trial.
2. Be  $\geq 18$  years of age on day of signing informed consent.
3. Presence of MRD (defined as  $< 5\%$  blasts in the bone marrow by morphologic assessment and no clinically-apparent extramedullary disease but with quantifiably-measurable disease as assessed by either MFC or PCR) under any of the following circumstances:
  - a. MRD persistence  $\geq 11$  weeks after the start of initial therapy,
  - b. MRD persistence  $\geq 2$  weeks after the start of salvage therapy, or
  - c. MRD reappearance at any time.

9458- Protocol Version Date 28 Feb 2019

4. For patients with Ph+ disease, have previously received treatment with  $\geq 1$  ABL kinase inhibitor (e.g., imatinib, dasatinib, etc.) or are ineligible for such treatment.
5. Have previously received or are ineligible for treatment with blinatumomab. Ineligibility will include (but not be limited to) CD19-negative disease, denial of insurance coverage, physician discretion, and/or patient refusal.
6. Be willing to provide tissue from a newly obtained bone marrow aspirate and/or biopsy. Newly-obtained is defined as a specimen obtained up 28 days prior to initiation of treatment on Day 1. Subjects for whom newly-obtained samples cannot be provided (e.g., inaccessible or subject safety concern) may submit an archived specimen only upon agreement from the PI.
7. Have a performance status of 0 to 1 on the ECOG Performance Scale.
8. Demonstrate adequate organ function as defined in Table 1, all screening labs should be performed within 10 days of treatment initiation.

Table 1: Adequate Organ Function Laboratory Values

System	Laboratory Value
Hematological	
Absolute neutrophil count (ANC)	$\geq 1,000$ /mCL
Hemoglobin	$\geq 8$ g/dL
Platelets	$\geq 50,000$ / mCL
Renal	
Serum creatinine OR Measured or calculated a creatinine clearance (GFR can also be used in place of creatinine or CrCl)	$\leq 1.5$ X upper limit of normal (ULN) OR $\geq 60$ mL/min/1.73 m  for subject with creatinine levels $> 1.5$ X institutional ULN
Hepatic	
Serum total bilirubin	$\leq 1.5$ X ULN OR Direct bilirubin $\leq$ ULN for subjects with total bilirubin levels $> 1.5$ ULN
AST (SGOT) and ALT (SGPT)	$\leq 2.5$ X ULN
Coagulation	
International Normalized Ratio (INR) or Prothrombin Time (PT)	$\leq 1.5$ X ULN unless subject is receiving anticoagulant therapy as long as PT or PTT is within therapeutic range of intended use of anticoagulants
Activated Partial Thromboplastin Time (aPTT)	$\leq 1.5$ X ULN unless subject is receiving anticoagulant therapy as long as PT or PTT is within therapeutic range of intended use of anticoagulants
a Creatinine clearance or glomerular filtration rate (GFR) should be calculated per the MDRD equation: GFR (mL/min/1.73 m  ) = $175 \times (S_{cr})^{-1.154} \times (Age)^{-0.203} \times (0.742 \text{ if female}) \times (1.212 \text{ if African American})$	

9. Female subjects of childbearing potential should have a negative urine or serum pregnancy within 3 days prior to receiving the first dose of study medication. If the urine test is positive or cannot be confirmed as negative, a serum pregnancy test will be required. (For this protocol, childbearing potential is defined in section 5.7.2.)

9458- Protocol Version Date 28 Feb 2019

10. Female subjects of childbearing potential should be willing to use 2 methods of birth control or be surgically sterile, or abstain from heterosexual activity for the course of the study through 120 days after the last dose of study medication (Reference Section 5.7.2).
11. Male subjects should agree to use an adequate method of contraception (as defined in section 5.7.2) starting with the first dose of study therapy through 120 days after the last dose of study therapy.

### 5.1.3 Subject Exclusion Criteria

The subject must be excluded from participating in the trial if the subject:

1. Is currently participating and receiving study therapy or has participated in a study of an investigational new drug and received study therapy or used an investigational device within 4 weeks of the first dose of treatment.
2. Has a diagnosis of immunodeficiency or is receiving systemic steroid therapy or any other form of immunosuppressive therapy within 7 days prior to the first dose of trial treatment.
3. Has a known history of active TB (Bacillus Tuberculosis).
4. Has a known hypersensitivity to pembrolizumab or any of its excipients.
5. Has had a prior anti-cancer monoclonal antibody (mAb) within 4 weeks prior to study Day 1 or who has not recovered (i.e.,  $\leq$  Grade 1 or at baseline) from adverse events due to agents administered more than 4 weeks earlier.
6. Has had prior chemotherapy, targeted small molecule therapy, or radiation therapy within 2 weeks prior to study Day 1 or who has not recovered (i.e.,  $\leq$  Grade 1 or at baseline) from adverse events due to a previously administered agent.
  - Note: Subjects with  $\leq$  Grade 2 neuropathy or with hematologic toxicity that has recovered to levels above that stated in Inclusion Criterion 6 are an exception to this criterion and may qualify for the study if all other inclusion/exclusion criteria are met.
  - Note: If subject received major surgery, they must have recovered adequately from the toxicity and/or complications from the intervention (i.e.,  $\leq$  Grade 1 or at baseline) prior to starting therapy.
7. Has a known additional malignancy that is progressing or requires active treatment. Exceptions include basal cell carcinoma of the skin or squamous cell carcinoma of the skin that has undergone potentially curative therapy or in situ cervical cancer.
8. Has known active central nervous system (CNS) leukemia and/or leukemic meningitis. Subjects with previously treated CNS leukemia may participate provided they are stable (e.g., without evidence of active disease by imaging for at least four weeks prior to the first

9458- Protocol Version Date 28 Feb 2019

dose of trial treatment and any neurologic symptoms have returned to baseline) and have no evidence of leukemic blasts on analysis of cerebrospinal fluid (CSF).

9. Has active autoimmune disease that has required systemic treatment in the past 2 years (i.e. with use of disease modifying agents, corticosteroids or immunosuppressive drugs). Replacement therapy (eg., thyroxine, insulin, or physiologic corticosteroid replacement therapy for adrenal or pituitary insufficiency, etc.) is not considered a form of systemic treatment.
10. Has known history of, or any evidence of active, non-infectious pneumonitis.
11. Has previously received an allogeneic hematopoietic cell transplant, unless the following criteria are met:
  - Detection of MRD occurred  $\geq$  21 days from stem cell infusion
  - No active GVHD
  - Receiving systemic steroid therapy of  $\leq$  10 mg of prednisone daily (or equivalent)
  - Has discontinued systemic immunosuppressant therapy  $\geq$  7 days prior to first dose of pembrolizumab
12. Has previously received other forms of cellular immunotherapy (e.g., chimeric antigen receptor-modified [CAR] T cells), unless the following criteria are met:
  - Detection of MRD occurred  $\geq$  21 days from cell infusion
  - Any specific manifestations of cytokine release syndrome or neurologic toxicity attributable to the cellular therapy have completely resolved (i.e.,  $<$  Grade 1)
13. Has an active infection requiring systemic therapy. Antimicrobial prophylaxis will be permitted at the discretion of the treating investigator.
14. Has a history or current evidence of any condition, therapy, or laboratory abnormality that might confound the results of the trial, interfere with the subject's participation for the full duration of the trial, or is not in the best interest of the subject to participate, in the opinion of the treating investigator.
15. Has known psychiatric or substance abuse disorders that would interfere with cooperation with the requirements of the trial.
16. Is pregnant or breastfeeding, or expecting to conceive or father children within the projected duration of the trial, starting from the time of consent through 120 days after the last dose of trial treatment.
17. Has received prior therapy with any immune checkpoint inhibitor.
18. Has a known history of Human Immunodeficiency Virus (HIV) (HIV 1/2 antibodies).

9458- Protocol Version Date 28 Feb 2019

19. Has known active Hepatitis B (e.g., HBsAg reactive) or Hepatitis C (e.g., HCV RNA [qualitative] is detected).
20. Has received a live vaccine within 30 days of planned start of study therapy.

*Note: Seasonal influenza vaccines for injection are generally inactivated flu vaccines and are allowed; however intranasal influenza vaccines (e.g., Flu-Mist®) are live attenuated vaccines, and are not allowed.*

## 5.2 Trial Treatments

The treatment to be used in this trial is outlined below in Table 2

Table 2: Trial Treatment

Drug	Dose/Potency	Dose Frequency	Route of Administration	Regimen/Treatment Period	Use
Pembrolizumab	200 mg	Q 21±3 days	IV infusion	Day 1 of each 21-day cycle	Experimental

Trial treatment should begin within 28 days of signed informed consent.

### 5.2.1 Dose Selection/Modification

#### 5.2.1.1 Dose Selection

The rationale for selection of doses to be used in this trial is provided in Section 4.0 – Background and Rationale.

Details on preparation and administration of pembrolizumab (MK-3475) are provided in the Pharmacy Manual.

#### 5.2.1.2 Dose Modification

AEs associated with pembrolizumab exposure may represent an immunologic etiology. These immune-related AEs (irAEs) may occur shortly after the first dose or several months after the last dose of pembrolizumab treatment and may affect more than one body system simultaneously. Therefore, early recognition and initiation of treatment is critical to reduce complications. Based on existing clinical study data, most irAEs were reversible and could be managed with interruptions of pembrolizumab, administration of corticosteroids and/or other supportive care. For suspected irAEs, ensure adequate evaluation to confirm etiology or exclude other causes. Additional procedures or tests such as bronchoscopy, endoscopy, skin biopsy may be included as part of the evaluation. Based on the severity of irAEs, withhold or permanently discontinue pembrolizumab and administer corticosteroids. Dose modification and toxicity management guidelines for irAEs associated with pembrolizumab are provided in Table 3.

Table 3: Dose Modification Guidelines for Drug-Related Adverse Events

General instructions:				

 
1. Corticosteroid taper should be initiated upon AE improving to Grade 1 or less and continue to taper over at least 4 weeks.
 
2. For situations where pembrolizumab has been withheld, pembrolizumab can be resumed after AE has been reduced to Grade 1 or 0 and corticosteroid has been tapered. Pembrolizumab should be permanently discontinued if AE does not resolve within 12 weeks of last dose or corticosteroids cannot be reduced to <math>\leq 10</math> mg prednisone or equivalent per day within 12 weeks.
 
3. For severe and life-threatening irAEs, IV corticosteroid should be initiated first followed by oral steroid. Other immunosuppressive treatment should be initiated if irAEs cannot be controlled by corticosteroids.
 
				
Immune-related AEs	Toxicity grade or conditions (CTCAEv5.0)	Action taken to pembrolizumab	irAE management with corticosteroid and/or other therapies	Monitor and follow-up
Pneumonitis	Grade 2	Withhold	
 
• Administer corticosteroids (initial dose of 1-2 mg/kg prednisone or equivalent) followed by taper
 
	
 
• Monitor participants for signs and symptoms of pneumonitis
 
• Evaluate participants with suspected pneumonitis with radiographic imaging and initiate corticosteroid treatment
 
• Add prophylactic antibiotics for opportunistic infections
 

	Grade 3 or 4, or recurrent Grade 2	Permanently discontinue		
Diarrhea / Colitis	Grade 2 or 3	Withhold	
 
• Administer corticosteroids (initial dose of 1-2 mg/kg prednisone or equivalent) followed by taper
 
	
 
• Monitor participants for signs and symptoms of enterocolitis (ie, diarrhea, abdominal pain, blood or mucus in stool with or without fever) and of bowel perforation (ie, peritoneal signs and ileus).
 
• Participants with <math>\geq</math> Grade 2 diarrhea suspecting colitis should consider GI consultation and performing endoscopy to rule out colitis.
 
• Participants with diarrhea/colitis should be advised to drink liberal quantities of clear fluids. If sufficient oral fluid intake is not feasible, fluid and electrolytes should be substituted via IV infusion.
 

	Grade 4	Permanently discontinue		
AST / ALT elevation or Increased bilirubin	Grade 2	Withhold	
 
• Administer corticosteroids (initial dose of 0.5- 1 mg/kg prednisone or equivalent) followed by taper
 
	
 
• Monitor with liver function tests (consider weekly or more frequently until liver enzyme value returned to baseline or is stable)
 

	Grade 3 or 4	Permanently discontinue		

9458- Protocol Version Date 28 Feb 2019

			prednisone or equivalent) followed by taper	
Type 1 diabetes mellitus (T1DM) or Hyperglycemia	Newly onset T1DM or Grade 3 or 4 hyperglycemia associated with evidence of $\beta$ -cell failure	Withhold	
 
Initiate insulin replacement therapy for participants with T1DM
 
Administer anti-hyperglycemic in participants with hyperglycemia
 
	
 
Monitor participants for hyperglycemia or other signs and symptoms of diabetes.
 

Hypophysitis	Grade 2	Withhold	
 
Administer corticosteroids and initiate hormonal replacements as clinically indicated.
 
	
 
Monitor for signs and symptoms of hypophysitis (including hypopituitarism and adrenal insufficiency)
 

	Grade 3 or 4	Withhold or permanently discontinue 		
Hyperthyroidism	Grade 2	Continue	
 
Treat with non-selective beta-blockers (eg, propranolol) or thionamides as appropriate
 
	
 
Monitor for signs and symptoms of thyroid disorders.
 

	Grade 3 or 4	Withhold or permanently discontinue 		
Hypothyroidism	Grade 2-4	Continue	
 
Initiate thyroid replacement hormones (eg, levothyroxine or liothyronine) per standard of care
 
	
 
Monitor for signs and symptoms of thyroid disorders.
 

Nephritis and Renal dysfunction	Grade 2	Withhold	
 
Administer corticosteroids (prednisone 1-2 mg/kg or equivalent) followed by taper.
 
	
 
Monitor changes of renal function
 

	Grade 3 or 4	Permanently discontinue		
Myocarditis	Grade 1 or 2	Withhold	
 
Based on severity of AE administer corticosteroids
 
	
 
Ensure adequate evaluation to confirm etiology and/or exclude other causes
 

	Grade 3 or 4	Permanently discontinue		
All other immune-related AEs	Intolerable/persistent Grade 2	Withhold	
 
Based on type and severity of AE administer corticosteroids
 
	
 
Ensure adequate evaluation to confirm etiology and/or exclude other causes
 

	Grade 3	Withhold or discontinue based on the type of event. Events that require discontinuation include and not limited to: Guillain-Barre Syndrome, encephalitis		

9458- Protocol Version Date 28 Feb 2019

	Grade 4 or recurrent Grade 3	Permanently discontinue		

1. Withhold or permanently discontinue pembrolizumab is at the discretion of the investigator or treating physician.
 
NOTE: For participants with Grade 3 or 4 immune-related endocrinopathy where withhold of pembrolizumab is required, pembrolizumab may be resumed when AE resolves to <math>\leq</math> Grade 2 and is controlled with hormonal replacement therapy or achieved metabolic control (in case of T1DM).
				

Dosing interruptions are permitted in the case of medical / surgical events or logistical reasons not related to study therapy (e.g., elective surgery, unrelated medical events, patient vacation, and/or holidays). Subjects should be placed back on study therapy within 3 weeks of the scheduled interruption, unless otherwise discussed with Merck. The reason for interruption should be documented in the patient's study record.

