### **7.1.3 Laboratory Procedures/Assessments**

Details regarding specific laboratory procedures/assessments to be performed in this trial are provided below.

Laboratory tests for hematology, chemistry, urinalysis, and others are specified in Table 5.

9458- Protocol Version Date 28 Feb 2019

Table 5: Laboratory Tests

Hematology	Chemistry	Urinalysis	Other
Hematocrit	Albumin	Blood	Serum $\beta$ -human chorionic gonadotropin†
Hemoglobin	Alkaline phosphatase	Glucose	( $\beta$ -hCG)†
Platelet count	Alanine aminotransferase (ALT)	Protein	PT (INR)
WBC (total and differential)	Aspartate aminotransferase (AST)	Specific gravity	aPTT
Red Blood Cell Count	Lactate dehydrogenase (LDH)	Microscopic exam ( If abnormal, results are noted )	Total triiodothyronine (T3)
Absolute Neutrophil Count	Carbon Dioxide	Urine pregnancy test †	Free thyroxine (T4)
Absolute Lymphocyte Count	( CO2 or biocarbonate )		Thyroid stimulating hormone (TSH)
	Uric Acid		
	Calcium		
	Chloride		Blood for correlative studies
	Glucose		
	Phosphorus		
	Potassium		
	Sodium		
	Magnesium		
	Total Bilirubin		
	Direct Bilirubin ( If total bilirubin is elevated above the upper limit of normal )		
	Total protein		
	Blood Urea Nitrogen		

† Perform on women of childbearing potential only. If urine pregnancy results cannot be confirmed as negative, a serum pregnancy test will be required.

9458- Protocol Version Date 28 Feb 2019

Laboratory tests for screening or entry into the Second Course Phase should be performed within 10 days prior to the first dose of treatment. After Cycle 1, pre-dose laboratory procedures can be conducted up to 3 days prior to dosing. Results must be reviewed by the investigator or qualified designee and found to be acceptable prior to each dose of trial treatment.

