### **7.1.5.3 Post-Treatment Visits**

#### **7.1.5.3.1 Safety Follow-Up**

Subjects with an AE of Grade > 1 will be followed until the resolution of the AE to Grade 0-1 or until the beginning of a new anti-neoplastic therapy, whichever occurs first. SAEs that occur within 90 days of the end of treatment or before initiation of a new anti-cancer treatment (whichever comes first) should also be followed and recorded.

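### Table 3 withholds pembrolizumab for Grade 1 myocarditis, but its general restart rule allows dosing at Grade 1, and nothing says which prevails

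*Combined protocol and SAP*

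**What the plan says.** Section 5.2.1.2 puts three general instructions at the head of Table 3, followed by event-specific rows.

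- **Restart.** General instruction 2 states that, where drug has been withheld, "pembrolizumab can be resumed after AE has been reduced to Grade 1 or 0 and corticosteroid has been tapered".
- **Time limit.** The same instruction continues: "Pembrolizumab should be permanently discontinued if AE does not resolve within 12 weeks of last dose", or if the steroid cannot be brought down to 10 mg of prednisone or equivalent per day in that time. No grade is attached to the word *resolve*.
- **Taper.** General instruction 1: "Corticosteroid taper should be initiated upon AE improving to Grade 1 or less and continue to taper over at least 4 weeks".
- **Myocarditis row.** "Myocarditis Grade 1 or 2 Withhold". Grade 3 or 4 means permanent discontinuation. The row asks for corticosteroids according to severity and for adequate evaluation. It gives no restart condition.
- **The only event-specific restart rule.** The note under the table: "For participants with Grade 3 or 4 immune-related endocrinopathy where withhold of pembrolizumab is required, pembrolizumab may be resumed when AE resolves to" Grade 2 or less, with hormonal replacement or metabolic control.

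Section 5.6.1, the supportive care guidelines, has no myocarditis entry.

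**The concern.** By holding drug at Grade 1, the Myocarditis row is stricter than any other graded hold in the table. The generic restart rule does not carry that strictness through to recovery. A subject held for Grade 2 myocarditis who improves to Grade 1 and completes any taper meets the terms of instruction 2 while still at a grade the row lists as a reason to withhold. Two investigators could follow the same table and act differently.

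What is at stake is the safety of an individual subject: a dose given during ongoing cardiac immune toxicity. The response endpoint, the two-stage design and the early-relapse stopping rule are untouched.

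**Working it through.** The plan gives no figure to reproduce. The check compares each row's withhold grades with the general restart range of Grade 0–1.

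| Table 3 row | Grades with a withhold action | Inside Grade 0–1? |
|---|---|---|
| Pneumonitis | 2 | no |
| Diarrhea/colitis | 2, 3 | no |
| AST/ALT or bilirubin | 2 | no |
| T1DM/hyperglycemia | 3, 4 (new-onset T1DM has no grade) | no; T1DM cannot be tested |
| Hypophysitis | 2; 3, 4 optional | no |
| Hyperthyroidism | 3, 4 optional | no |
| Hypothyroidism | none | not applicable |
| Nephritis/renal | 2 | no |
| **Myocarditis** | **1, 2** | **yes, at Grade 1** |
| All other irAEs | 2 if intolerable or persistent; 3 by event type | no |

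Ten rows, nine with a withhold action, one overlap.

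**Is there an override for myocarditis?** None in the row and none in Section 5.6.1. The note under the table covers endocrinopathy only. That note does create a comparable overlap: hypophysitis is held at Grade 2, yet a Grade 3 or 4 event may restart at Grade 2 or less. But it says so openly and adds a control condition.

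**Does the 12-week clause close the gap?** It depends on what *resolve* means, and the protocol does not use the idea uniformly:

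- Section 7.1.5.3.1 accepts Grade 0–1: "Subjects with an AE of Grade > 1 will be followed until the resolution of the AE to Grade 0-1".
- Exclusion 12 in Section 5.1.3 sets a level below Grade 1: "Any specific manifestations of cytokine release syndrome or neurologic toxicity attributable to the cellular therapy have completely resolved".
- The note under Table 3 uses Grade 2 or less.

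If *resolve* means Grade 0–1, persistent Grade 1 never triggers the clause. If it means Grade 0, restart can still come first. For a steroid-treated event, taking *tapered* to mean taper completed:

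- minimum taper = 4 × 7 = 28 days after Grade 1 is reached;
- clause acts at 12 × 7 = 84 days after the last dose;
- 84 − 28 = 56, so an event that reaches Grade 1 within 56 days of the last dose can finish a minimum taper, and qualify for restart at Grade 1, by the time the clause acts.

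**Do the other safeguards set a restart grade?**

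- Section 7.1.3: "Results must be reviewed by the investigator or qualified designee and found to be acceptable prior to each dose of trial treatment". Table 5 lists no cardiac test.
- The flow chart in Section 6.1 schedules adverse event review and a directed examination each cycle. It names no cardiac procedure.
- Section 5.8 ends treatment for unacceptable adverse experiences, but defines them by pointing back to Section 5.2.1.2. Investigator withdrawal is discretionary.
- Table 6 requires advance approval to rechallenge after a serious, possibly drug-caused event, or where re-exposure adds potential significant risk. It too refers back to the dose modification guidelines.

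Each lowers the chance of re-dosing at Grade 1. None forbids it.

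**The case against.** The strongest case against is that onset triggers and recovery thresholds do different jobs. Instruction 2 expressly governs withheld drug, so myocarditis does have a restart rule, and the endocrinopathy note shows the table tolerating a similar pattern. If instead the specific row outranks the general instruction, Grade 1 stays on hold and the gap vanishes. Harm needs the less protective reading and an investigator who chooses to restart. The Table 6 approval requirement may well catch the case under its significant-risk limb. All of this stands, and it is why the point is an overlap and a minor one. It does not tell the investigator which reading applies.

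It is also fair that Grade 1 or less is the protocol's usual recovery standard. Exclusions 5 and 6 and the surgery note in Section 5.1.3 use Grade 1 or baseline, and adverse event follow-up ends at Grade 0–1. Exclusion 12 is an exception and concerns toxicity from a different prior therapy. Grade 0 is therefore a choice and not something the protocol already requires.

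A reader might infer three stronger things that the documents do not support:

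- **That Table 3 contradicts itself.** The onset-versus-recovery reading reconciles the two instructions.
- **That the worse event has the looser rule,** because an event starting at Grade 1 cannot be *reduced to* Grade 1 and so must reach Grade 0. That rests on parsing one phrase; no text states it.
- **That the risk has a known size.** The documents give neither a myocarditis rate nor the share of cases that would follow this path.

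The myocarditis grade definitions are not reproduced either, so what Grade 1 means clinically after a Grade 2 event cannot be checked here.

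**Conclusion.** The point holds as an internal overlap in a safety rule. One of nine withholding rows has a hold grade inside the general restart range, no precedence is stated, and the plan can be read to allow a dose during ongoing Grade 1 myocarditis. The conclusion assumes that instruction 2 applies to myocarditis, as its general wording indicates, and that a Grade 2 event can be graded as improved to Grade 1. Severity is minor: restart is permissive, discretionary checks make it unlikely, and no endpoint, sample size or analysis is affected.

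**What to change.** Add to the Myocarditis row of Table 3:

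*Restart only when myocarditis has resolved to Grade 0, evaluation is complete and any corticosteroid has been tapered. General instruction 2 does not permit restart at Grade 1. Discontinue permanently if Grade 0 is not reached within 12 weeks of the last dose.*

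The reason for Grade 0 is that the restart level should lie below the row's own lowest hold grade.

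The cost is one line by amendment, with no extra patients or scheduled visits. In an affected subject, confirming Grade 0 may mean repeating the evaluation the row already asks for. The downside is that such a subject may stay off drug longer or have to discontinue.
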